
Protocol: Pilot trial of dronabinol adjunctive treatment of agitation in Alzheimer's disease (AD) (THC-AD)

Protocol Number: IRB00052955

Protocol Version: 6.0/2July2020

There is a great need for better interventions that target Agit-AD, a major source of patient disability as well as caregiver burden and stress, particularly in the case of moderate to severe agitation. This pilot trial could open the door to “repurposing” dronabinol as a novel and safe treatment for Agit-AD with significant public health impact.

2. Specific Aims:

We propose THC-AD: a three-week placebo-controlled, double-blind, randomized clinical trial of dronabinol (10 mg QD) in 80 patients with severe Agit-AD. Concomitant medications will be limited to currently used antipsychotics, antidepressants, benzodiazepines, as well as anticonvulsant therapy when not used for seizure disorder, with lorazepam 0.75 QD total daily allowed as rescue medication, and can be administered orally or intramuscularly. Additionally, these four categories of currently used concomitant medications are permitted to be used with PRN trazodone in doses up to 100 mg total daily dose for agitation and insomnia.

AIM 1: To compare the efficacy of three weeks of dronabinol adjunctive treatment to placebo in 80 patients with severe Agit-AD.

Hypothesis 1: Compared to placebo, dronabinol treatment will be associated with a greater reduction in symptoms of agitation as measured by co-primary outcomes of a) PAS b) NPI-C Agitation, Aggression, and the sum of Agitation and Aggression. The Cohen-Mansfield Agitation Inventory will be a secondary agitation outcome. Psychosocial function, cognition, and sleep will be assessed for potential benefit.

AIM 2: To compare the safety of three weeks of dronabinol adjunctive treatment to placebo in 80 patients with severe Agit-AD.

Hypothesis 2: Dronabinol treatment will be well tolerated with (AEs) not significantly different than placebo, including incident delirium as measured by the Confusion Assessment Method (CAM).

Outcomes:

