All AEs occurring after randomization and during the 3-week treatment period, regardless of adherence to study treatment, will be recorded at all contacts. AEs will be assessed by using all available data to determine if new symptoms or medical events have occurred. A list of common side effects of dronabinol will be used to monitor for adverse events. At scheduled visits, participants and clinical staff/family caregivers will be interviewed about whether the participant experienced any symptoms or side effects on the list since the last visit. Adverse events, other than what is listed as common side effects, will still be recorded. If adverse events are noted, they will be rated as mild, moderate, or severe based on their clinical severity and frequency. Finally, medical transfers to outside general hospitals (McLean) or to a medical/surgical unit in the same hospital (Johns Hopkins and Miami Jewish Health) will be monitored. The PIs and designated study physicians will be responsible for monitoring the safety of participants. They will be responsible for appropriate medical care of participants during the study in connection with

Protocol: Pilot trial of dronabinol adjunctive treatment of agitation in Alzheimer's disease (AD) (THC-AD)
Protocol Number: IRB00052955 **Protocol Version:** 6.0/2July2020

study procedures. Safety assessments will include physical exams, vital signs, ECGs, monitoring of adverse events, and monitoring and maintenance of concurrent medication records. AEs will be reported to the local IRBs per local policy. Serious adverse events (SAEs) will be defined per FDA guidelines and reported in a timely manner as is standard in clinical trials (with the initial report being next business day). In addition, we will add the following DSMB-agreed upon SAEs to the SAE definition:

- 1) Death (already defined as an SAE per standard FDA guidelines)
- 2) Delirium at two consecutive weekly assessments
- 3) Seizures
- 4) Fall resulting in injury

In accordance to FDA reporting requirements, any serious adverse events (SAEs) that occur at Johns Hopkins, Miami Jewish Health, and McLean Hospital will be reported to Johns Hopkins and [name], M.D., the Sponsor-Investigator. Expected SAEs include delirium, intoxication, sedation, and increased appetite. Such reporting will adhere to the following process:

- 1) Sponsor-Investigator will be notified of the SAE and will be given a report

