Medical History	X				
Other Medications	X				
Randomization		X			
Study medication dispensing		X	X	X	
Coronavirus Impact Scale (CIS)		X			
Unblinding*					X *
Clinical Instruments					
Pittsburgh Agitation Scale (PAS)		X	X	X	X
Neuropsychiatric Inventory, Clinician Version (NPI-C)		X	X	X	X
Cohen-Mansfield Agitation Inventory (CMAI)		X	X	X	X
Modified Alzheimer's Disease Cooperative Study- Clinical Global Impression of Change (CGI-C)		X	X	X	X
Alzheimer's Disease Cooperative Study - Activities of Daily Living (ADCS-ADL)		X	X	X	X
Confusion Assessment Method (CAM)		X	X	X	X
Sleep Assessment (NPI-C Sleep Subscale)		X	X	X	X
Cognition					
SIB-8		X			X
Mini Mental State Exam (MMSE)		X			X
Drug Effect					
Drug Effect Questionnaire (DEQ)		X	X	X	X
Medication Side-Effects Questionnaire		X	X	X	X
Safety and AE monitoring					
Physical Exam	X				
Neurological Exam	X				
Vital Signs		X	X	X	X
General Medical Health Rating (GMHR)	X				
Adverse Event Monitoring		X	X	X	X
ECG		X			X
Blood draw (DNA, Biomarker, CBC, CMP, TSH)		X			X

*Only done after all other study procedures are complete

Protocol: Pilot trial of dronabinol adjunctive treatment of agitation in Alzheimer's disease (AD) (THC-AD)

Protocol Number: IRB00052955

Protocol Version: 6.0/2July2020

6. **Biostatistical Analysis:**

All analyses will be conducted using STATA (55) and R (56) under the supervision of the study statistician ([name]). Descriptive analyses will be conducted and measures checked for outliers and to ensure that distributional assumptions of the planned analyses are appropriate. If not, analogous non-parametric methods will be used. Analyses will be intent-to-treat. We expect minimal missing data, but if there is a significant amount of missing data, multiple imputation may be used if appropriate (57). To investigate sensitivity to missing values, those with and without missing values will be compared by background covariates. Tests will be two-sided and p-values <0.05 will be considered significant.

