Multiple test corrections will be applied as appropriate. All primary analyses will be adjusted for site as well as the variables balanced through minimization (use of antidepressants and use of antipsychotics). To account for the inclusion of multiple sites, we will include site as a covariate, with individuals being seen on an outpatient (largely remote) basis being treated as its own site. Secondarily, we will fit models with site, site x time, and site x treatment x time to determine if there are any effects of site on treatment effect over time. These analyses must be secondary as the study was not powered to detect these 3 way interactions. Importantly, no participants were stopped during their participation and all participants will have the same mode of assessment (either in-person or remote) throughout.

Aim 1: Efficacy will be assessed by fitting a longitudinal linear model with the co-primary outcomes (PAS and NPI-C Agitation/Aggression/Sum of Agitation and Aggression) and with time, treatment assignment and interaction between time and treatment. The latter term will be the coefficient of interest and will represent the mean difference in change over the 3-week period between the treated and placebo groups. Within-person correlations will be handled via the method of generalized estimating equations (58).

Aim 2: We will model risk of a severe adverse event as a function of treatment assignment using logistic regression, and counts of total adverse events using ordinal logistic regression or poisson regression as appropriate. We will also scrutinize counts of each specific type of AE as a function of treatment assignment to determine if there are specific adverse events which we should power ourselves to detect in future larger-scale trials. Special attention will be paid to new-onset delirium, seizures, and arrhythmias. Additionally we will specifically look at the effect of dronabinol on cognition using the SIB-8, and a regression model analogous to that in Aim 1. We will stratify adverse events by site and assess whether rates of particular AEs vary by site. In particular, we will assess whether outpatients differ in their rates and types of AEs (either favorably, due to being less acute, or unfavorably, due to a less controlled environment where falls might be more likely, for example).

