Secondary Analyses: We will model change in additional outcomes (e.g., CMAI, MMSE, sleep, DEQ) using models analogous to that of Aim 1. We will also look at predictors of dronabinol response, including cannabinoid receptor polymorphisms and other patient characteristics. We will also model change in IL1 β , TNF α , and IL6 as a function of treatment assignment. All secondary analyses will be conducted with site as a covariate, and additional analyses which include site x treatment and site x treatment by time will be performed.

Sample size and Power analysis

Protocol: Pilot trial of dronabinol adjunctive treatment of agitation in Alzheimer's disease (AD) (THC-AD)

Protocol Number: IRB00052955

Protocol Version: 6.0/2July2020

We observed a large effect in our observational study that used PAS as outcome. PAS is one of the co-primary outcomes and we will estimate power to detect change in PAS. There are no pilot data to estimate power to detect change in NPI-C which has not been used in prior trials of dronabinol. The PAS declined in our observational study from 9.68 (3.91) pre-treatment to 5.25 (4.17) post-treatment for a treatment effect of 1.1 and 45% reduction in PAS score.

We propose to use a more conservative estimate of 30% reduction in PAS score and calculated statistical power using the formulae of Jung and Ahn (59). A 30% reduction translates to decreasing from 9.68 PAS points to 7.26 points after 3 weeks, which means a slope of -0.81 points/week. This translates to an effect size of 0.206. It is essential to account for missing data including those from dropouts. Assuming first a missing data pattern that increases monotonically to 15% by week 3, with N= 80, a within-person correlation of 0.5 and an exchangeable correlation structure, we will have 80% power to detect a treatment effect of size 0.22, which translates to a decrease in PAS from 9.68 to 7.1 over 3 weeks; this is a 26.7% decrease. Assuming next a missing data pattern that increases monotonically to 30% by week 3, then with 80 people and a within-person correlation of 0.5 and an exchangeable correlation structure, we would have 80% power to detect a treatment effect of size 0.24, which translates to a decrease in PAS from 9.68 to 6.87 over 3 weeks; this is a 29.1% decrease. Thus, THC-AD is well-powered to detect a clinically plausible and conservatively estimate decrease in PAS which is a co-primary outcome.

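### Hypothesis 2 rests tolerability on a non-significant AE comparison, which about 40 patients per arm cannot support for a single uncommon binary event

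*Combined protocol and SAP*

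**What the plan says.** Aim 2 (section 2) is a comparison of safety between dronabinol and placebo over three weeks. Its hypothesis is: "Dronabinol treatment will be well tolerated with (AEs) not significantly different than placebo, including incident delirium as measured by the Confusion Assessment Method (CAM". The general standard in section 6 is: "Tests will be two-sided and p-values <0.05 will be considered significant".

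The Aim 2 paragraph of section 6 names the models. For severe events: "We will model risk of a severe adverse event as a function of treatment assignment using logistic regression". Total AE counts go to ordinal logistic or Poisson regression. Each AE type is also examined, partly to identify "specific adverse events which we should power ourselves to detect in future larger-scale trials". The paragraph adds "Special attention will be paid to new-onset delirium, seizures, and arrhythmias", an analysis of SIB-8, and "We will stratify adverse events by site and assess whether rates of particular AEs vary by site". Under Safety and Adverse Event monitoring (section 5), "All AEs occurring after randomization and during the 3-week treatment period, regardless of adherence to study treatment, will be recorded at all contacts".

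The sample size section covers efficacy only: "PAS is one of the co-primary outcomes and we will estimate power to detect change in PAS". No section gives an expected AE rate, a safety margin, an interval criterion or power for an AE endpoint.

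**The concern.** Hypothesis 2 is the only sentence that connects the comparative AE results to the words well tolerated, and it does so through absence of significance. A hypothesis of that form is easier to confirm the smaller or noisier the trial is. For delirium, seizure or arrhythmia, which may be uncommon over three weeks, failing to reject is the likely result whether or not dronabinol raises the risk.

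At stake is the safety conclusion in a population that the protocol itself calls frail. A null comparison on delirium or severe AEs could be reported as tolerability although the data remain compatible with a large excess.

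**Working it through.** **The plan's own power figure.** The only stated power is for PAS: 80% at effect size 0.22, with N = 80, missingness rising to 15% by week 3, and exchangeable correlation 0.5. The GEE slope formula that the plan cites, with visits at weeks 0 to 3 and linear monotone missingness, gives 81.6% at 0.22 and a smallest detectable effect of 0.2156, which rounds to 0.22. The figure reproduces, but it says nothing about AEs.

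**Inputs.** 80 randomised (section 3) at close to 1:1 (Randomization and blinding), so about 40 per arm; two-sided 0.05 (section 6). Assumed, because the documents give none: the 3-week placebo rate, and a doubling as the excess of interest.

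**Approximate check, 10% v 20%.** Pooled rate 0.15.
- SE under no difference = √(2 × 0.15 × 0.85 / 40) = 0.0798.
- SE under the alternative = √((0.10 × 0.90 + 0.20 × 0.80) / 40) = 0.0791.
- Power = Φ((0.10 − 1.96 × 0.0798) / 0.0791) = Φ(−0.715) = 0.24, so about 76% non-significant. For 80% power, 199 per arm would be needed.

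**Exact enumeration of two binomials, 40 per arm: chance of a non-significant result.** The Wald column is the unadjusted version of the planned logistic model, with zero cells counted as non-significant.

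| Placebo v drug | Chi-square | Fisher | Logistic Wald |
|---|---|---|---|
| 5% v 10% | 85.4% | 95.7% | 98.3% |
| 10% v 20% | 75.3% | 83.8% | 82.3% |
| 15% v 30% | 63.4% | 71.9% | 65.6% |
| 20% v 40% | 50.3% | 59.2% | 50.5% |
| 30% v 60% | 20.4% | 27.5% | 20.4% |
| 10% v 30% (tripling) | 36.8% | 46.6% | 42.1% |

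Non-significance stops being the more likely result of a doubling at a placebo rate of about 20% (chi-square or Wald) to 23% (Fisher). At the plan's fallback of N = 60 (30 per arm), 10% v 20% is non-significant 81-90% of the time (chi-square to Fisher). No multiplicity correction is modelled; one would raise these figures.

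**What an interval would show.** The Newcombe upper limit for drug minus placebo is d + √((U₁ − p₁)² + (p₀ − L₀)²), where L and U are Wilson limits. In percentage points, the Wilson limits for 4/40 are 3.96 and 23.05.
- 4/40 in each arm: 0 + √(13.05² + 6.04²) = 14.4.
- 8/40 on drug v 4/40: 10 + √(14.76² + 6.04²) = about 26; p = 0.21 (chi-square), 0.35 (Fisher).
- 10/40 on drug v 4/40: 15 + √(15.19² + 6.04²) = about 31; p = 0.077, 0.139.
- 0/40 in each arm: about 9, where a Wald interval would have zero width.

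All of these results are non-significant and would fit Hypothesis 2 as worded.

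**Total AE counts, for contrast.** A doubling from 1 to 2 events per patient (assumed), Poisson: SE of the log rate ratio = √(1/40 + 1/80) = 0.194, so power = Φ(0.693/0.194 − 1.96) = about 95%. If the variance is twice the mean, SE = 0.274 and power is about 72%.

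**The case against.** The best defence is that the plan never states the inference complained of. Hypothesis 2 is an expectation, Aim 2 is simply to compare safety, and section 6 looks to later trials for power on specific AEs, as befits a pilot. Safety also rests on total counts, scrutiny by AE type, SIB-8, added SAE definitions and unblinded DSMB review. All of this stands and limits the point. None of it says what a non-significant comparison means, and deferring AE power to later trials sits badly with a hypothesis that non-significance confirms.

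The rates and the doubling are assumptions, and the result depends on them: at 30% v 60% most trials would reach significance, as they would for a tripling from 10%. That also stands.

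Four stronger readings are tempting but unsupported:
- *The plan has a rule declaring dronabinol safe when p exceeds 0.05.* No such rule is written.
- *The trial cannot detect harm.* The count analysis is fairly sensitive. If two independent endpoints both double, both are missed 57-70% of the time at a 10% placebo rate but only 25-35% at 20%.
- *The PAS missingness of 15% or 30% shrinks the AE comparison further.* AEs are recorded whether or not treatment is taken, so that loss could apply at most to scheduled CAM assessments.
- *Delirium is common, given the 56% quoted in section 3.* That is a lifetime prevalence in dementia, not a 3-week incidence.

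**Conclusion.** The concern holds for single, uncommon binary safety endpoints. At about 40 per arm, and for assumed placebo rates of 5% to 20%, a true doubling is non-significant at least half the time, and 75-84% of the time at 10% v 20%. Even identical observed rates of 10% leave an excess of about 14 points unexcluded. Non-significance on delirium, seizure, arrhythmia or severe AEs therefore cannot carry the conclusion that Hypothesis 2 attaches to it. The point does not extend with the same force to common events or total counts, and it is not a charge that safety goes unmonitored. The change should be made: it alters what the trial can legitimately conclude, at little cost.

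**What to change.** Restate Hypothesis 2 as estimation of the excess risk of AEs on dronabinol over placebo, and add to the Aim 2 paragraph of section 6:

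> For any severe AE, incident CAM-positive delirium, seizure, arrhythmia and fall with injury, we will report the 3-week risk difference (dronabinol minus placebo) with a 95% Newcombe interval, alongside the planned models. A non-significant difference will not be read as evidence of tolerability. The safety conclusion will state the largest excess risk that the interval does not exclude.

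For delirium, do not count missing CAM assessments as event-free in the main estimate. That pulls towards no excess, most of all if dropout is heavier on drug. As an illustration, take 4 events per arm with 12 drug-arm patients unassessed. Counting them as event-free gives 4/40 v 4/40 and an upper limit of 14.4 points. Among those assessed, 4/28 v 4/40 gives 4.29 + √(17.20² + 6.04²) = about 22.5 points. Instead:
- report CAM completeness by arm and visit;
- base the main estimate on observed CAM data plus delirium recorded as an AE;
- use the multiple imputation that section 6 already allows if missingness is material;
- show a sensitivity range for the missing assessments.

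The cost is one reworded hypothesis, one added paragraph and one small table. Data collection, SAE definitions, planned models and sample size do not change. The downside is wide intervals and a more cautious safety conclusion, which is proportionate in a pilot.

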Participants will be recruited at clinical sites associated with McLean Hospital, Johns Hopkins University, and Miami Jewish Health Services. Referrals will come from physicians on these units following standard IRB procedures and maintaining confidentiality per HIPAA standards. Specifically, referring physicians will obtain consent from participants or legally authorized representatives (i.e. family with power of attorney or who serve as the patient's health care proxy) to make the referral. Then participants and/or families will be approached by research staff per standard IRB-approved procedures.

4. Participant Enrollment:

At the informed consent/screening visit, a member of the study staff will go through the informed consent form with the participants, and if appropriate, delegates. The participants and/or legal authorized representative will be encouraged to ask any questions they may have regarding study related procedures before the consent form is signed. Study staff will provide adequate time for the potential participant to consider participation in the study. Study staff will continue to emphasize that participation is voluntary and may be stopped at any time after signing consent without affecting their ability to receive treatment at McLean Hospital, Johns Hopkins Hospital, Miami Jewish Health, or any other institute. Potential participants who decide to participate in the study will document their consent by signing and dating the consent. All consents will be obtained by trained study clinicians.

Before participants sign the consent form, an independent clinician will meet with the participants to assess their capacity to make informed decisions about participating in this study and complete the competency/capacity evaluation form. In the case the participant is deemed unable to give consent for the study, a legal representative may consent on their behalf.

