The investigators will be blind to treatment assignment. The Research Pharmacy will prepare blind medication using opaque capsules and randomly assign eligible participants to dronabinol vs. placebo treatment. We will use minimization to ensure that treatment groups are balanced with respect to use of antidepressant and antipsychotics. This method is preferred over stratification for trials of small sample size (38). The goal is have a ratio of drug:placebo close to 1:1 but adjust over time to achieve balance of antidepressant and antipsychotic use between the dronabinol and placebo groups. To address concerns that future or past randomizations could be predicted based on knowledge of treatment assignment of any one participant (relevant to unblinding at the end of the study for ethical reasons), we will use dynamic, non-deterministic probabilities of treatment assignments (39). User-friendly software to perform this type of minimization has already been developed and used by our research group in several R01-supported clinical trials including “Pilot Trial of Carvedilol in AD” and “Venlafaxine for depression in AD”. Note that although the odds of assignment to treatment group may vary across the course of the study, treatment assignment still remains a randomized process and the investigators remain blind to treatment assignment. The Research Pharmacy will keep treatment assignment confidential but have access to treatment assignment available on a 24-hour basis. In the event of medical emergency where knowledge of treatment assignment is essential to providing safe patient care, the Research Pharmacy will inform treating physicians of the treatment assignment. The investigators will be kept blind to treatment assignment except in extreme cases. In the event of unmasking, the Research Pharmacist will make a report to the DSMB.

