Medication Side-Effects Questionnaire		X	X	X	X
Safety and AE monitoring					
Physical Exam		X			
Neurological Exam		X			
Vital Signs		X	X	X	X
General Medical Health Rating (GMHR)	X				
Adverse Event Monitoring		X	X	X	X
ECG		X			X
Blood draw (DNA, Biomarker, CBC, CMP, TSH)		X			X

*Only done after all other study procedures are complete.

Outpatient Enrollment – Procedures Color Legend:	
Completed in-person	
Completed remotely via HIPAA compliant video software	
Completed via optional location (in-person or remote)	

Unmasking:

Every effort will be made to maintain the masked nature of the trial while taking precautions to optimize participant safety. Unmasking of treatment assignment before 3 weeks (“emergency unmasking”) will be limited to medical situations in which withholding knowledge of the identity of the drug will lead to unreasonable danger or suffering, and will not be necessary for routine management of potential side effects. The Research Pharmacy will have 24-hour access to treatment unmasking information. In an emergency situation, the study physician may elect to unmask a participant’s treatment assignment. All participants will undergo treatment unmasking at the endpoint of the study. This will either be at the Week 3 visit, or earlier if study treatment is discontinued prior to the third week. Participants and their referring physicians will be informed of treatment assignment after unmasking.

5. Participant Procedures:

Following the informed consent process, each participant will complete assessments conducted by the study coordinator and the principal investigator or delegated study staff member. The specific assessments conducted are detailed below. The participant’s participation will be comprised of 4 visits spanning their 3-week study enrollment. The study procedures per visit are outlined in Table 2.

- **Coronavirus Impact Scale (CIS):** The CIS is a short, 12-item scale that rates the influence of the Coronavirus (COVID-19) pandemic on multiple health factors, including employment, access to healthcare, and stress. The CIS was developed by [name] MAS, and [name].

Clinical Assessments

- **Pittsburgh Agitation Scale (PAS) (40) (Co-primary outcome):** The PAS was developed for both

Protocol: Pilot trial of dronabinol adjunctive treatment of agitation in Alzheimer’s disease (AD) (THC-AD)
Protocol Number: IRB00052955 **Protocol Version:** 6.0/2July2020

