In any drug study there is the risk that the study team will obtain data that might be interpreted as hinting at treatment assignment particularly due to observation of AEs, and that the observation of outcomes will become biased due to this awareness. This is a common issue in AD pharmaceutical industry trials. We will adopt the strategy of splitting up the members of the team who assess primary outcomes from those who assess AEs. Primary outcomes will be assessed by research assistants and/or coordinators. Outcomes that encompass subjective effects of drug exposure and/or AEs will be assessed by study physicians and/or nurses. These two teams will not exchange any information obtained and thus will be blinded to each other's findings. Combined with the fact that all study/clinical staff are blind to treatment assignment, this will ensure that observation of outcomes will remain unbiased.

10. References:

1. Alzheimer's Association 2014 Alzheimer's disease facts and figures. *Alzheimer's & Dementia*. Elsevier; 2014 Mar 1;10(2):e47–e92.

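### Routine Week 3 unmasking, with on-unit referring physicians told, conflicts with the statement that all clinical staff are blind, and the plan does not say who is shielded from it

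*Combined protocol and SAP*

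**What the plan says.** Section 4, Unmasking, makes disclosure routine: "All participants will undergo treatment unmasking at the endpoint of the study". The timing is individual: "This will either be at the Week 3 visit, or earlier if study treatment is discontinued prior to the third week". The recipients are named: "Participants and their referring physicians will be informed of treatment assignment after unmasking". Tables 1 and 2 both list unblinding as a Week 3 procedure, with a footnote placing it after everything else at that visit.

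The recruitment text in section 3 identifies the referrers: "Referrals will come from physicians on these units".

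Section 4, Randomization and blinding, says "The investigators will be kept blind to treatment assignment except in extreme cases". It also mentions knowledge of assignments as "relevant to unblinding at the end of the study for ethical reasons", and answers that with non-deterministic assignment probabilities.

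Section 9, Blind maintenance plan, splits the team. Research assistants or coordinators rate the primary outcomes, physicians or nurses rate drug effects and adverse events, and the two groups do not share findings. It adds that "all study/clinical staff are blind to treatment assignment" and concludes that outcome observation will stay unbiased.

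**The concern.** Dronabinol has visible effects. The part of section 4 on blinded rating accepts that seeing them can reveal treatment and bias outcome assessment. A clinician who sees a patient for three weeks and is then told the assignment gets feedback on what active treatment looks like. With repeated feedback, that clinician can recognise it better in the next patient. If such clinicians, or colleagues they talk to, supply information on later participants, those ratings become less blind as the trial proceeds. The PAS and NPI-C are observer judgements, so the co-primary outcomes have little protection if the leak reaches their raters.

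**Working it through.** No figure in the plan bears on this point, so the check sets the statements side by side.

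1. **Who learns what, and when.** Every participant's assignment is released at the end of that person's participation, not at database lock. The participant and the referring physician are told. Referring physicians are on the recruiting units, so some clinical staff know true assignments during the trial. The section 9 statement that clinical staff are all blind is therefore not true as written.

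2. **Does enrolment overlap with this?** No accrual period is stated. Section 9 plans DSMB meetings every 6 months and annual rater retraining, which implies a trial of well over three weeks. Section 4 also worries that one known assignment could help predict future ones, which matters only if randomization continues. As an illustration, with uniform accrual over W weeks the share randomized after the first routine unmasking is 1 − 3/W:
   - 12 months: 1 − 3/52 = 94%
   - 24 months: 1 − 3/104 = 97%
   - 48 months: 1 − 3/208 = 99%

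   The durations are assumptions. These are trial-wide upper figures: on any one unit, exposure begins only when that unit's own first participant is unmasked.

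3. **Who is shielded?** Section 5 has assessments conducted by the coordinator and the principal investigator or a delegate, and section 9 lets coordinators rate primary outcomes. The visit tables list unblinding without saying who carries it out or who must not see the result. Section 4 says that investigators stay blind but gives no mechanism for the Week 3 step.

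4. **Do the safeguards cover this route?** Non-deterministic minimization stops a known assignment from revealing another. It does nothing about recognising drug effects. The rater split separates two groups of study staff and does not extend to unit clinicians. Clinical staff supply information for the ADCS-ADL where necessary (section 5, Clinical Assessments) and for the drug-effect and side-effect questionnaires (section 5, Drug effect monitoring). Under Inpatient Enrollments and Remote Assessments, the team may also interview healthcare providers remotely using the same forms, which may extend to other ratings.

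5. **Whose data are exposed?** A completer's assessments are finished before unblinding, so they are unaffected. The exposure is to later participants on the same units.

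6. **Early discontinuation.** Section 4 limits unmasking before 3 weeks to situations of unreasonable danger or suffering, but also unmasks anyone whose treatment stops early. Section 5 records adverse events through 3 weeks whatever the adherence, and section 6 analyses by intent to treat. Data after an early stop could therefore be collected with the assignment known.

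**The case against.** A reader might infer that routine unmasking flatly contradicts the rule that investigators stay blind except in extreme cases. The documents do not support that. The sentence directly follows the provision for medical emergencies, the same paragraph openly anticipates unblinding at the end, and Unmasking names only participants and referring physicians as recipients. Nothing says that referrers are investigators, or that raters are told. What remains is a gap: the plan does not say how the investigators stay blind.

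The plan also has a real safeguard in the rater split, which targets recognition of treatment from its effects and must be given credit. No passage says that referring physicians are informants for the PAS or NPI-C, or that they pass assignments to colleagues. For outpatients, information comes from a caregiver who would normally see one participant and learn the assignment afterwards, so recognition would not carry over. These points limit the concern mainly to inpatient and long-term care units.

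The section 9 statement could be read as meaning blind to the participant being rated, which would be true for completers. That is narrower than its wording, and it would not by itself support the assurance that outcomes stay unbiased.

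**Conclusion.** The point holds as a conflict between Unmasking in section 4 and the Blind maintenance plan in section 9, together with an unstated procedure for keeping investigators, raters and unit informants away from the Week 3 unblinding. It rests on two inferences: that enrolment continues while earlier participants are unmasked, which is very probable, and that on-unit clinicians who learn assignments may influence information on later participants, which is plausible but not stated for the co-primary scales.

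The size of any bias cannot be computed. The documents give no accrual period, no patients per unit, no count of informed clinicians and no measure of how well treatment can be recognised. A reader might infer that the PAS comparison is biased by some number of points, or that upcoming assignments can be guessed. The documents support neither: any point value would be invented, and the non-deterministic minimization is aimed at the second.

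Separately, the two rules on unmasking before 3 weeks do not fit together and must be reconciled.

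**What to change.** Keep the ethical disclosure and change its route:

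- The Research Pharmacy, which already holds the assignments, tells the participant or representative and the physician responsible for continuing care directly.
- Enrolling investigators, primary outcome raters and, as far as possible, unit staff who act as informants stay masked until database lock.
- Remove unblinding from Tables 1 and 2 as a visit procedure of the research team, and state in section 4 who performs it and who is shielded.
- Correct the section 9 statement so that it claims only the blinding the procedures deliver.
- Reconcile, within Unmasking, the limit on release before 3 weeks with release at early discontinuation, taking account of continued adverse event recording and the intent-to-treat analysis.

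The cost is a procedural amendment and some pharmacy handling, with no extra participants or assessments. Containment will be imperfect where the continuing-care physician works on the enrolling unit, and the amended text should say so.
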